### **4.1 Monitoring**

The sponsor has engaged the services of a contract research organization (CRO), [REDACTED], to perform all monitoring functions within this clinical study. [REDACTED] monitors will work in accordance with [REDACTED] SOPs and have the same rights and responsibilities as monitors from the sponsor organization. Monitors will establish and maintain regular contact between the investigator and the sponsor.

Monitors will evaluate the competence of each study site, informing the sponsor about any problems relating to facilities, technical equipment or medical staff. During the study, monitors will check that written informed consent has been obtained from all patients correctly and that data are recorded correctly and completely. Monitors are also entitled to compare entries in eCRFs with corresponding source data and to inform the investigator of any errors or omissions. Monitors will also control adherence to the protocol at the study

site. They will arrange for the supply of investigational product and ensure appropriate storage conditions are maintained.

Monitoring visits will be conducted according to all applicable regulatory requirements and standards. Regular monitoring visits will be made to each site while patients are enrolled in the study. The monitor will make written reports to the sponsor on each occasion contact with the investigator is made, regardless of whether it is by phone or in person.

During monitoring visits, entries in the eCRFs will be compared with the original source documents (source data verification). For the following items, this check will be 100%:

- Subject number.
- Patient consent obtained.
- Patient eligibility criteria (inclusion and exclusion criteria).
- Efficacy variables.
- Medical record of AE.

## **4.2 Data Management/Coding**

Data generated within this clinical study will be handled according to the relevant SOPs of the Data Management and Biostatistics departments of [REDACTED].

Electronic Data Capture (EDC) will be used for this study, meaning that all eCRF data will be entered in electronic forms at the study site. Data collection will be completed by authorized study site staff designated by the investigator. Appropriate training and security measures will be completed with the investigator and all authorized study site staff prior to the study being initiated and any data being entered into the system for any study patients.

All data must be entered in English. The eCRFs should always reflect the latest observations on the patients participating in the study. Therefore, the eCRFs are to be completed as soon as possible during or after the patient's visit.

The investigator must verify that all data entries in the eCRFs are accurate and correct. If some assessments are not done, or if certain information is not available or not applicable or unknown, the investigator should indicate this in the eCRF. The investigator will be required to electronically sign off on the clinical data.

The monitor will review the eCRFs and evaluate them for completeness and consistency. The eCRF will be compared with the source documents to ensure that there are no discrepancies between critical data. All entries, corrections and alterations are to be made by the responsible investigator or his/her designee. The monitor cannot enter data in the eCRFs. Once clinical data of the eCRF have been submitted to the central server, corrections to the data fields will be audit trailed, meaning that the reason for change, the name of the person who performed the change, together with time and date will be logged. Roles and rights of the site staff responsible for entering the clinical data into the eCRF will be determined in

advance. If additional corrections are needed, the responsible monitor or Data Manager will raise a query in the EDC application. The appropriate study site staff will answer queries sent to the investigator. This will be audit trailed by the EDC application meaning that the name of investigational staff, time and date stamp are captured.

The eCRF is essentially considered a data entry form and should not constitute the original (or source) medical records unless otherwise specified. Source documents are all documents used by the investigator or hospital that relate to the patient's medical history, that verify the existence of the patient, the inclusion and exclusion criteria and all records covering the patient's participation in the study. They include laboratory notes, ECG results, memoranda, pharmacy dispensing records, patient files, etc.

The investigator is responsible for maintaining source documents. These will be made available for inspection by the study monitor at each monitoring visit. The investigator must submit a completed eCRF for each patient who receives study medication, regardless of duration. All supportive documentation submitted with the eCRF, such as laboratory or hospital records, should be clearly identified with the study and patient number. Any personal information, including patient name, should be removed or rendered illegible to preserve individual confidentiality.

The eCRF records will be automatically appended with the identification of the creator, by means of their unique User ID. Specified records will be electronically signed by the investigator to document his/her review of the data and acknowledgement that the data are accurate. This will be facilitated by means of the investigator's unique User ID and password; date and time stamps will be added automatically at time of electronic signature. If an entry on an eCRF requires change, the correction should be made in accordance with the relevant software procedures. All changes will be fully recorded in a protected audit trail, and a reason for the change will be required.

AEs will be coded using Medical Dictionary for Regulatory Activities (MedDRA) version 19.0. Concomitant medications will be coded using WHO-DDE. Concomitant diseases/medical history will be coded using MedDRA.

### **4.3 Retention of Records**

Records and documents pertaining to the conduct of this study and the distribution of IMP, including eCRFs, ICFs, laboratory test results, and medication inventory records, must be retained by the principal investigator (Japan: Head of study site) for at least 15 years after completion or discontinuation of the study, or for the length of time required by relevant national or local health authorities, whichever is longer. After that period of time, the documents may be destroyed, pertinent to local regulations. No records may be disposed of without the written approval of the sponsor. Written notification should be provided to the sponsor prior to transferring any records to another party or moving them to another location.

#### **4.4 Quality Assurance Audit**

Study sites, the study database and study documentation may be subjected to Quality Assurance audit during the course of the study by the sponsor or delegate(s) on behalf of the sponsor. In addition, inspections may be conducted by regulatory bodies at their discretion.

#### **4.5 Site Audits**

The principal investigator or sub-investigators and institutions involved in the study will permit study-related monitoring, audits, IRB review, and regulatory inspection(s) by providing direct access to all study records. In the event of an audit, the principal investigator or sub-investigator agrees to allow the sponsor, its representatives, or the regulatory agencies access to all study records.

The investigator should promptly notify the sponsor or its authorized representative of any audits scheduled by any regulatory authorities and promptly forward copies of any audit reports received to the sponsor or its authorized representative.

## **5.0 STATISTICS**

### **5.1 General Statistical Considerations**

Protocol HBI-8000-210 is a Phase 2b Open-Label Single-Arm Study to Evaluate the Efficacy and Safety of Oral HBI-8000 in Patients with Relapsed or Refractory Adult T-Cell Lymphoma (ATL). The main analysis will be conducted for the purpose of regulatory submission of this product. The data cut-off (DCO) for the main analysis is set at the time when the last patient completes at least one post-efficacy assessment. The eCRF data by the DCO needs to be cleaned to have no unresolved queries. All independent reviews (including the independent radiological review, the Independent Overall Efficacy Review and review by the Data Safety Monitoring Board) by the DCO need to be completed before the main analysis. The data after the main analysis will be provided at the end of the study as a supportive material.

Statistical analysis for all safety, and efficacy parameters will be primarily descriptive in nature. Categorical variables will be summarized by frequency distributions (number and percentages of patients), continuous variables will be summarized by mean, standard deviation, median, minimum, maximum, and time-to-event variables will be summarized using Kaplan-Meier methods and figures for the estimated median time.

All analyses, summaries, and listings will be performed using Statistical Analysis System software (version 9.3 or higher)

A detailed methodology for summary and statistical analysis of the data collected in this trial will be documented in a statistical analysis plan (SAP) that will be dated and maintained by HUYA Biosciences. The SAP may modify the plans outlined in the protocol; however, any major modifications of the primary endpoint definition and/or its analysis will also be reflected in a protocol amendment.

### **5.2 Determination of Sample Size**

For efficacy determination, 18 patients evaluable for efficacy per protocol criteria are required. To ensure meeting this target, 22 patients would be enrolled if 20% of patients are assumed not to complete required study treatment or evaluations for efficacy determination. Enrolled patients will be treated with the starting dose of 40 mg BIW to provide an assessment of tumor response as well as additional safety data.

The target best ORR for this study is 30%, on the basis of the ORR results that were obtained in study TG0902CDM. The power for showing the response rate >5% at 5% two-sided alpha in 18 patients is 80%.

### **5.3 Treatment Assignment and Blinding**

This is an open-label, sequential enrollment study; therefore, no randomization or blinding procedures will be performed.

## **5.4 Replacement of Patients**

Patients who are lost to follow-up or withdraw consent for study participation prior to receiving HBI-8000 or who withdraw in Cycle 1 for reasons unrelated to drug toxicity or PD will be replaced.

## **5.5 Populations for Analysis**

### **5.5.1 Safety Population**

The safety analyses population will include all patients who receive at least 1 dose of HBI-8000. The safety analyses population will be the primary population for evaluating treatment administration / compliance and safety in the study.

### **5.5.2 Efficacy Population**

Efficacy should be analyzed using FAS and PPS.

The FAS is defined as Patients meeting all eligibility criteria and having received at least one dose of study medication, and at least one efficacy assessment of disease with either imaging studies or clinical examination after receiving study medication.

The PPS is defined as Patients meeting all eligibility criteria and having completed Cycle 1 treatment or discontinued study treatment during cycle 1 due to clinical PD. It should be noted that the PPS includes subjects who discontinue within Cycle 1 due to clinical PD without imaging studies to assess disease status.

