Statistical Procedures:	

Statistical analysis for all safety and efficacy parameters will be primarily descriptive in nature. Categorical variables will be summarized by frequency distributions (number and percentages of patients), continuous variables will be summarized by mean, standard deviation, median, minimum, and maximum, and time-to-event variables will be summarized using Kaplan-Meier methods and figures for the estimated median time. A formal statistical analysis plan will be completed prior to database lock and any study-related analyses.
 
Efficacy should be analyzed by Full analysis set (FAS) and Per protocol set (PPS). The FAS is defined as Patients meeting all eligibility criteria and having received at least one dose of study medication, and at least one efficacy assessment of disease with either imaging studies or clinical examination after receiving study medication.
	

The PPS is defined as Patients meeting all eligibility criteria and having completed Cycle 1 treatment or discontinued study treatment during cycle 1 due to clinical PD. It should be noted that the PPS includes subjects who discontinue within Cycle 1 due to clinical PD without imaging studies to assess disease status. For efficacy determination, 18 patients evaluable for efficacy per protocol criteria are required. To ensure meeting this target, 22 patients would be enrolled if 20% of patients are assumed not to complete required study treatment or evaluations for efficacy determination. Enrolled patients will be treated with the starting dose of 40 mg BIW to provide an assessment of tumor response as well as additional safety data.

The target best ORR for this study is 30%, on the basis of the ORR results that were obtained in study TG0902CDM. The power for showing the response rate  $>5\%$  at 5% two-sided alpha in 18 patients is 80%.

Any patient that has received any amount of study medication will be considered as evaluable for safety. Safety data will be summarized with descriptive statistics and frequency tables and will include AEs, hematology, coagulation, serum chemistry, urinalysis, vital signs, and ECG data. Laboratory values will be summarized by numerical value and toxicity grade.

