### 2.6.1 Screening Assessments (within 28 days prior to start of treatment)

Written informed consent for participation in the study must be obtained before performing any study specific screening tests or evaluations. Informed Consent Forms (ICFs) for all patients screened (whether enrolled or not) will be maintained at the study site.

All screening and baseline assessments must be completed and reviewed to confirm that patients meet all eligibility criteria. An Eligibility Screening Form documenting the investigator's assessment of each screened patient with regard to the protocol's inclusion and exclusion criteria is to be completed and kept at the study site.

Screening assessments include medical history and concomitant medications, documentation of ATL diagnosis in accordance with the WHO revised classification [WHO 2008] and treatment history. Screening assessments will be performed within 28 days prior to Cycle 1 Day 1 (C1D1). A pretreatment bone marrow test (aspiration or biopsy) would be required. Results of standard-of-care tests or examinations performed prior to obtaining informed consent and within 28 days prior to C1D1 may be used (and do not need to be repeated for screening unless they do not meet the criteria defined in the protocol). Similarly, tumor assessment tests <2 weeks outside the 28-day window in the absence of clinical evidence of PD, the results may be accepted.

Women of childbearing potential must agree to practice contraceptive measures after signing informed consent. A negative serum pregnancy test will be obtained during screening.

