#### **2.6.4 End of Treatment Safety Follow-up Visit**

All patients receiving at least 1 dose of HBI-8000 and discontinuing treatment for any reason except death will be evaluated approximately 30 ( $\pm$  3) days after the last dosing of study drug or before the initiation of new cancer treatment, whichever is earlier. Any patient for whom study treatment has been discontinued should complete study procedures listed in the EoT visit. At EoT safety visit, evaluations will include physical examination, vital signs, body weight, ECOG performance status, hematology, blood chemistry, urinalysis, pregnancy test (if applicable), ECG, and assessment of any ongoing AEs. If a patient discontinues study

treatment before PD is recorded, and if the last tumor assessment was >30 days earlier from the EoT visit, tumor assessment should be performed at EoT. In these patients, further tumor assessments are to be performed approximately every 3 months  $\pm$  2 weeks until PD or the start of new cancer therapy whichever occurs first, unless consent to study participation is withdrawn.

Patients with HBI-8000-related AEs of Grade  $\geq$  2 observed at the EoT visit should be followed-up and monitored monthly (phone calls/clinic visits) until the AEs have resolved to Grade  $\leq$  1 or are determined to be chronic, or patient receives other anti-cancer therapy.

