#### **2.6.6 Patient Withdrawal**

Patients have the right to withdraw from the study at any time for any reason, and the investigator should try to ascertain the reason for withdrawal as completely as possible. The investigator also has the authority to decide whether a patient should be discontinued from the study. Study treatment may be discontinued and the patient withdrawn from the study under the following circumstances:

- Unacceptable toxicity (AE)
- Progression of the disease under study
- Decision by the investigator to permanently discontinue study drug administration
- Intercurrent illness that would, in the judgment of the investigator, affect clinical assessments, patient safety, or follow-up significantly
- Significant protocol deviations that jeopardize the usefulness of the data
- Repeated patient non-compliance
- Patient is beginning another anti-cancer treatment protocol
- Patient becomes pregnant
- Patient requests to withdraw informed consent
- Study termination by the sponsor

All patients who withdraw from study treatment must complete an EoT visit, to be performed  $30 \pm 3$  days after the last dosing of the study drug (see [Appendix A](#)) or before the initiation of

new cancer treatment, whichever is earlier. A patient may withdraw consent for treatment but still allow follow-up, in which case he/she should be followed for safety, survival, and disease status. If a patient has withdrawn consent to study participation entirely, no subsequent follow-up will be performed.

Patients who are lost to follow-up or withdraw consent for study participation prior to receiving HBI-8000 or who withdraw before completing Cycle 1 for reasons unrelated to drug AEs or PD will be replaced.

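### Eligible patients who die without progression or withdraw fully in Cycle 1 before any post-dose assessment are in neither efficacy set, and the protocol names no primary ORR set and no non-responder rule

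*Combined protocol and SAP*

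**What the plan says.** Section 5.5.2, repeated in the synopsis, defines two efficacy sets. Both require that the patient met every eligibility criterion.

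- FAS: at least one dose, plus "at least one efficacy assessment of disease with either imaging studies or clinical examination after receiving study medication".
- PPS: "having completed Cycle 1 treatment or discontinued study treatment during cycle 1 due to clinical PD". Patients who stop in Cycle 1 for clinical PD are kept even without imaging.

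Neither set is called primary. Section 5.5.1 names a primary population, but only for safety and treatment administration. Section 5.9 reports the ORR as a number and percentage with an exact 95% CI. Its sentence on the primary analysis settles who assesses response (central review), not which patients form the denominator. Table 8 has a not-assessable category but no rule for counting it.

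Several other provisions decide who gets a post-dose assessment:

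- The first scheduled tumor assessment is due by the end of week 4 (Section 2.6.3). Blood and skin lesions are evaluated on Day 1 of later cycles (Appendix D).
- The end-of-treatment (EoT) visit in Section 2.6.4 is for patients "discontinuing treatment for any reason except death". It takes place 30 ± 3 days after the last dose "or before the initiation of new cancer treatment, whichever is earlier".
- For patients who stop before PD, "if the last tumor assessment was >30 days earlier from the EoT visit, tumor assessment should be performed at EoT". Tumor follow-up about every 3 months comes after that (Sections 2.6.4 and 2.6.5, Table 4).
- For a patient who has "withdrawn consent to study participation entirely, no subsequent follow-up will be performed" (Section 2.6.6).

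The synopsis adds: "A formal statistical analysis plan will be completed prior to database lock and any study-related analyses".

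**The concern.** In a single-arm trial the ORR depends directly on who is in the denominator. An unassessed patient contributes no response, so every such patient left out raises the estimate and both confidence limits; the error cannot go the other way. Section 5.1 says the main analysis is for regulatory submission, and with about 18 patients each one moves the rate visibly.

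The definitions also treat similar patients differently. A Cycle 1 stop for clinical PD without imaging counts as a failure in the PPS, while a Cycle 1 death without PD and without assessment counts nowhere. Because no primary set is named, the choice between FAS and PPS is also open in a trial where treatment and investigator-assessed outcome are known throughout.

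**Working it through.** **Step 1. Who falls outside both sets.** All cases are eligible, dosed, leave treatment in Cycle 1 without clinical PD, and have had no post-dose efficacy assessment. None is in the PPS.

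| Case | Route into the FAS? |
|---|---|
| Death | None: the EoT visit excepts deaths |
| Full withdrawal of consent | None: no follow-up afterwards |
| Early new therapy | EoT is brought forward, possibly to within 30 days of the screening scan, and later tumor follow-up ends; depends on whether the EoT physical examination is an accepted clinical examination |
| Stop after a single dose | Usually at EoT, otherwise at 3-month follow-up |
| Missed assessment | Usually at EoT or 3-month follow-up |
| Toxicity stop, last dose Day 4 or later, regular EoT visit | Yes, by the EoT scan rule |

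**Step 2. EoT timing behind the last rows.** The screening scan is on Day 0 or earlier.

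- Last dose on Day 4: EoT falls on Day 4 + 27 = 31 to Day 4 + 33 = 37. The gap from the scan is at least 31 days, so a tumor assessment is always called for.
- Last dose on Day 1: EoT falls on Day 28 to 34. The gap is 30 days or less only for EoT Day 28 with a scan on Day -2 to 0, Day 29 with Day -1 to 0, or Day 30 with Day 0. Even then the 3-month follow-up applies, and the FAS sets no time limit. The patient is lost only if death, new therapy, full withdrawal or the data cut-off in Section 5.1 comes first.

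**Step 3. The plan's own figure.** Section 5.2 gives 18 evaluable patients, a target ORR of 30%, a reference rate of 5%, two-sided alpha of 5% and power of 80%. With the exact binomial test (upper tail at most 0.025):

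- P(X ≥ 3 | 18, 0.05) = 0.0581 and P(X ≥ 4 | 18, 0.05) = 0.0109, so 4 responders are needed.
- P(X ≥ 4 | 18, 0.30) = 0.835. With 17 patients it is 0.798.

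So 18 is the right size for a nominal 80%.

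**Step 4. Effect on the ORR.** The number affected is not stated. I assume 1 to 4 unassessed patients added to 18. The upper value is 22 - 18 = 4, from the enrolment allowance; it is an extreme, because that allowance covers every reason for loss. With 4 responders and Clopper-Pearson limits:

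| Denominator | ORR | Exact 95% CI |
|---|---|---|
| 18 | 22.2% | 6.4 to 47.6 |
| 19 | 21.1% | 6.1 to 45.6 |
| 20 | 20.0% | 5.7 to 43.7 |
| 21 | 19.0% | 5.4 to 41.9 |
| 22 | 18.2% | 5.2 to 40.3 |

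A 30% rate in 18 evaluable patients becomes 0.30 × 18/N: 28.4% at N = 19 and 24.5% at N = 22.

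**Step 5. Effect on the conclusion.** The lower limit for 4 responders stays above 5% up to N = 22. At N = 23 it is 4.95%. Starting from 18, the conclusion changes only with exactly 4 responders and at least 5 patients left out. False-positive risk is not inflated in this range either: if the true rate in 22 dosed patients is 5% and 4 are dropped, the rate in the other 18 is 0.05 × 22/18 = 6.1%, and P(X ≥ 4 | 18, 0.061) = 0.0214, below 0.025.

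**Step 6. Power for the wider set.** The overall rate is 0.30 × 18/N.

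- N = 22, 4 unassessed: rate 24.5%, P(X ≥ 4) = 82.6%.
- N = 23, 5 unassessed: rate 23.5%, threshold 5, P(X ≥ 5) = 65.7%.

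**The case against.** The strongest defence has five parts.

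- **The group is small.** Entry requires a life expectancy above 3 months and ECOG 0 to 2, PD may be declared on clinical judgement, and an examination in Cycle 1 may count as an assessment. This stands as a limit on size. It does not place a patient who dies before any assessment in either set.
- **The SAP may settle it.** Section 5.1 leaves detailed methodology to the SAP, which is not in the supplied text, so the gap is shown for the protocol only. However, the protocol does define the sets, and that definition, followed as written, excludes these patients. Section 5.1 also wants major changes to the primary analysis in an amendment.
- **Central review is blinded.** That protects the classification of response. It does not restore patients missing from the denominator.
- **Full withdrawals are replaced (Section 5.4) and disposition is tabulated (Section 5.5.3).** Replacement keeps the numbers up but does not decide whether the replaced patient counts. The tabulation helps a reader rebuild the rate but does not pre-specify it.
- **Sizing on evaluable patients was deliberate.** True, and the wider set has a cost in power. Naming a primary set and adding an all-dosed sensitivity analysis would show the effect, but would leave a primary estimate that early failures can only push upward.

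Two stronger readings are tempting. A reader might infer that Cycle 1 toxicity stoppers in general vanish from the efficacy analysis. The documents do not support that: the EoT scan rule and the 3-month follow-up bring most of them into the FAS. A reader might also infer that the gap could by itself produce a false finding of a rate above 5%. At 18 to 22 patients it does not.

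**Conclusion.** The point holds and should be fixed. As the protocol stands, a dosed, eligible patient who dies without clinical PD, or withdraws fully, in Cycle 1 before any post-dose efficacy assessment is in neither efficacy set. Early switchers to new therapy join them if the EoT physical examination does not count as an assessment. The protocol neither counts these patients as non-responders nor names a primary ORR set.

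The bias can only be upward. Under the assumed 1 to 4 patients and 4 responders it is about 1 to 4 percentage points (22.2% against 21.1% to 18.2%). The conclusion against 5% is unaffected at 18 to 22 patients. The literal reading of Section 5.5.2 is firm; the count is an assumption, and the announced SAP could narrow the gap.

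**What to change.** Before database lock, in Section 5.5.2 with matching text in the synopsis and the SAP:

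1. Name the FAS as the primary set for the ORR.
2. Remove its post-dose assessment condition, so that it holds all eligible patients who received at least one dose.
3. Count patients with no post-dose assessment, or a non-evaluable one, as non-responders.
4. Keep the PPS as supportive, report the ORR in all dosed patients as a sensitivity analysis, and list the patients excluded from each set with the reason.

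The cost is a protocol amendment and SAP wording; no new data are needed. The ORR will be slightly lower. The power statement in Section 5.2 must be given for the wider set: 83.5% at 18, and 82.6% at 22 if 4 are unassessed. Replaced patients who were dosed and eligible stay in the set. If that takes it to 23 with 5 unassessed, 5 responders are needed and power is 65.7%, below the planned 80%; the sponsor should acknowledge this when adopting the change.

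### The PPS keeps Cycle 1 stops for clinical PD but drops unreplaced Cycle 1 stops for drug toxicity, so the PPS response rate rests on an outcome-dependent denominator

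*Combined protocol and SAP*

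**What the plan says.** Section 5.5.2, repeated in the synopsis, asks for efficacy in two sets. The PPS takes eligible patients "having completed Cycle 1 treatment or discontinued study treatment during cycle 1 due to clinical PD". The FAS takes eligible patients with at least one dose and "at least one efficacy assessment of disease with either imaging studies or clinical examination after receiving study medication"; it does not require completion of Cycle 1. Neither set is named primary there or in section 5.9.

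Section 5.4 says that patients "who withdraw in Cycle 1 for reasons unrelated to drug toxicity or PD will be replaced". Section 2.6.6 has the same rule, worded as "who withdraw before completing Cycle 1 for reasons unrelated to drug AEs or PD will be replaced". Under both, a Cycle 1 stop for toxicity and a Cycle 1 stop for PD are treated alike: neither is replaced.

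Section 5.2 sets the size: "18 patients evaluable for efficacy per protocol criteria are required", and "22 patients would be enrolled if 20% of patients are assumed not to complete required study treatment or evaluations for efficacy determination". The power statement (target ORR 30%, reference rate 5%, two-sided alpha 5%, power 80%) is made for those 18.

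Section 2.6.9 and Table 1 contain rules under which treatment ends for toxicity, and these can apply within Cycle 1.

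**The concern.** Toxicity and progression in Cycle 1 are both outcomes of treatment, and the replacement rule recognises this. The PPS definition does not: it keeps the clinical-PD stop in the denominator and removes the toxicity stop. A patient whose treatment ends exactly as the protocol directs is thus left out of the per-protocol set because of a drug effect and not because of a protocol deviation.

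What is at stake is the meaning of the PPS ORR. It estimates response among patients who completed Cycle 1 or stopped for clinical PD, not among all eligible treated patients. With no primary set named, and with a sample-size sentence that may point to the PPS, this figure could be read as the main result of an analysis that section 5.1 intends for regulatory submission.

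**Working it through.** **1. The plan's own figure.** Inputs from section 5.2: n = 18, reference rate 5%, target 30%, two-sided alpha 5% (2.5% in the upper tail). Exact binomial rule: the smallest r with P(X ≥ r | 18, 0.05) ≤ 0.025.
- r = 3 gives 5.8%; r = 4 gives 1.09%. The rule is at least 4 responders.
- Power P(X ≥ 4 | 18, 0.30) = 83.5%. At n = 17, with the same r, it is 79.8%.

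So 18 is the smallest n that reaches 80%, and the sample size reproduces. For enrolment, 18 × 1.2 = 21.6, which rounds up to the stated 22. The margin is 22 − 18 = 4 patients.

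**2. Where each patient goes** (eligible, dosed)

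| Course in Cycle 1 | Replaced? | In PPS? | In FAS? |
|---|---|---|---|
| Completes | not applicable | yes | yes, if assessed after dosing |
| Stops for clinical PD | no | yes | yes, if assessed after dosing |
| Stops for drug toxicity | no | **no** | yes, if assessed after dosing |
| Withdraws for another reason | yes | no | yes, if assessed after dosing |

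Section 2.6.4 calls for an end-of-treatment visit, with a tumor assessment if the last one was more than 30 days earlier, so most toxicity stops should reach the FAS. One with no post-dose assessment falls out of both sets.

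**3. Effect on the estimate.** The documents give no rate of Cycle 1 toxicity stops. Assumption: k = 0 to 4 of 22 dosed, all non-responders, with 5 responders overall. PPS ORR = 5/(22 − k).

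| k | PPS ORR |
|---|---|
| 0 | 5/22 = 22.7% (exact 95% CI 7.8 to 45.4%) |
| 1 | 5/21 = 23.8% |
| 2 | 5/20 = 25.0% |
| 3 | 5/19 = 26.3% |
| 4 | 5/18 = 27.8% (exact 95% CI 9.7 to 53.5%) |

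The largest ratio is 22/18 = 1.22. In expectation, with a fraction t of non-responding toxicity stops, PPS ORR = all-treated ORR/(1 − t). A PPS ORR of 30% then corresponds to an all-treated ORR of 0.30 × 0.90 = 27.0% at t = 10%, and 0.30 × 0.80 = 24.0% at t = 20%.

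The direction depends on the assumption. If one of four toxicity stops were among the 5 responders, the PPS would give 4/18 = 22.2%, just below 22.7%.

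**4. Effect on the test against 5%.** Exact 95% lower limits:
- 4 responders: 6.4% (4/18), 5.7% (4/20), 5.2% (4/22), all above 5%.
- 3 responders: 3.6% (3/18), 2.9% (3/22), both below 5%.

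For a fixed number of responders the lower limit falls as n rises, so the end points settle every n from 18 to 22. Removing up to four non-responders from 22 cannot turn a failure into a success.

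With an all-treated ORR of 5%, the PPS rate is 0.05/(1 − t). At t = 20% this is 6.25%, and P(X ≥ 4 | 18, 0.0625) = 2.3%, against 1.1% at t = 0 and a limit of 2.5%.

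**The case against.** The strongest reply is that these patients are already covered. Both sets must be analysed, the FAS does not need Cycle 1 to be completed, and requiring a minimum exposure is an ordinary purpose of a per-protocol set. Replacement governs accrual and section 5.5.2 governs analysis, so the two rules need not match. This largely stands. A reader might infer that toxicity stops disappear from all efficacy analysis; the FAS definition does not support that. What remains is that the PPS is not made subordinate to a named primary set, and that it keeps one kind of early treatment failure while dropping another.

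A reader might also take the PPS to be the set that carries the power claim. Section 5.2 does not say so: its lower-case wording can mean evaluable by this protocol's criteria, and the losses it allows for include missing evaluations, which is an FAS criterion. The PPS reading is plausible but an inference.

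Nor is 1.22-fold an expected inflation. It gives the whole 20% allowance to toxicity, although ineligible patients and missed evaluations also draw on it. Table 1 holds and resumes dosing for many events, and section 1.8 describes the Grade 3 and 4 toxicities at 40 mg as transient and asymptomatic. Upward bias is not automatic either, since section 2.6.4 continues tumor assessment after an early stop and such a patient can be a responder.

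Finally, the word clinical before PD could be read as excluding PD seen on an early scan. That is strained: the next sentence of section 5.5.2 shows that the phrase is there to admit PD without imaging, and the first scheduled scan falls at about the end of Cycle 1.

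**Conclusion.** The point holds for the PPS estimate. Its denominator leaves out Cycle 1 toxicity stops, which are not replaced, while keeping clinical-PD stops. If toxicity stops respond less often than other patients, the PPS ORR is too high. Under the assumption of 0 to 4 non-responding stops among 22 dosed, 5 responders read as 22.7% to 27.8%, with 1.22-fold as a ceiling.

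The tempting stronger conclusion, that the definition could make the trial falsely positive against 5%, is not supported: the 4-responder threshold is the same at every n from 18 to 22, and the false-positive chance at n = 18 stays at or below 2.3% for stop rates up to 20%. This is a cheap improvement to an estimate, and it matters mainly because no primary set is named.

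**What to change.** In section 5.5.2 and the synopsis, and in the SAP to which section 5.1 refers, define the PPS as eligible patients who completed Cycle 1, or who discontinued study treatment in Cycle 1 because of PD or drug-related toxicity; count those who discontinued as non-responders unless a response was recorded. Leaving out the word clinical also removes any doubt about PD seen on imaging. The PPS then follows the same logic as sections 5.4 and 2.6.6, and toxicity stops count toward the 18 if that number is meant to refer to the PPS. Naming the primary efficacy set would complement this but is a separate change.

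The cost is one sentence in each place, with no change to dosing, stopping rules or data collection. The downside is a slightly lower PPS ORR and a PPS that differs less from the FAS, so it adds less as a separate analysis.
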